11. DATA HANDLING AND RECORD KEEPING

a. Data Collection and Management Responsibilities

- Screening, recruitment, consenting, delivery of interventions and data collection will be conducted by a trained Care Coordinator and is resource at 1 FTE for 8 months.
- Intervention formatting, ethical, financial, human resource, data management and assistance with 6 week phone follow-ups if required will be conducted by a Project Manager and is resourced at 0.8 then 0.4 FTE for 12 months.
- The expert advisory group will oversee all study processes, study reports and supervise study design and outcomes.

b. Study Records Retention

The Principal Investigator will maintain all records pertaining to this study for a period of 15 years from the date of publication.

University of Adelaide records, once created and captured, must not be damaged, altered or destroyed other than in accordance with General Disposal Schedules No 24 - South Australian Universities or an alternative Disposal Schedule, and with authorisation from the University Archivist or delegate in consultation with relevant business owners.

Responsibility: All employees, titleholders, consultants, contractors and volunteers of the University of Adelaide must:

- a. Create records that adequately document the activities and decisions of the University in which they take part, whether related to learning and teaching, research, commercialisation or administration;
- b. Capture important business records into the University recordkeeping system or an alternative business system with functionality to retain records in a secure manner for as long as they are legally required;
- c. Take appropriate steps to ensure the reliability of University records and ensure records can be located;
- d. Manage security of University records or restrict access if appropriate;
- e. Ensure records are described adequately to allow the University to store, dispose and/or archive them in accordance with academic, business and legal requirements; and
- f. Comply with legal requirements and standards including the State Records Act 1997, State Records Adequate Records Management Standards and the Australian Standard AS ISO 15489, as well as the University's procedures and processes in relation to records management.

c. Protocol Deviations

A protocol deviation is any noncompliance with the study protocol, Good Clinical Research Practice, or HREC requirements.

The noncompliance may be either on the part of the participant, the investigator, or the study site staff. As a result of deviations, corrective actions are to be implemented promptly.

The principal investigator will use continuous vigilance to identify and report deviations within 72 hours of identification of the protocol deviation. All deviations must be addressed in study source documents, reported to the approving HREC.

12. PUBLICATION & INTELLECTUAL PROPERTY

All existing Intellectual Property rights created by the University in the course of the REMIT-2-DS2 study vest in the University and on their creation, all future intellectual property rights created in the course of providing the study will also vest in the University.

The REMIT-2-DS2 Expert Advisory Group (**Appendix 2**) will be responsible for developing publication procedures and resolving authorship issues.

At the end of the study, the Principal Investigator will make results of the research available to participants, the research community and public at large.

It is anticipated that journal articles associated with the project may be submitted for publishing.

It is anticipated that study results will be made available on the SA Academic Health Science Translation Centre website and other relevant websites i.e. SA ACDC.

Dissemination of results to participants

The study results will be synthesised and presented in a form that is meaningful and applicable for clinicians, managers and policy makers to guide sustainable changes to systems and services within the SA hospital system to facilitate and drive the translation of that evidence into practice. Dissemination mechanisms and systems will be utilised that will make it easy for users (practitioners, managers, policy makers and consumers) to access the information/evidence generated by the study to facilitate the uptake of knowledge and drive system and behaviour change.

The dissemination of project outcomes will be designed to get the right message to the target audience. This will be achieved through a wide variety of dissemination methods including newsletters, flyers, and press releases to create awareness about the study, reports, journal articles, and web sites to transmit information about the study, and conference presentations and web sites to promote the study and its outcomes.

13. ETHICAL CONSIDERATIONS

a. Indemnity & Compensation for Injury

This study will be protected by an appropriate insurance and indemnity documentation arrangement to cover compensation for injury. The PI will provide supporting documentation to the Research Governance Organisation (RGO) including relevant insurance certificates and an email from Adelaide

University as the partnering organization with LMH- NALHN and TQEH and RAH- CALHN confirming that this study is covered by insurance. As an employee of Adelaide University, the Care Coordinator working with participants residing in a SA Health facility (LMH, TQEH, RAH), will be covered by appropriate insurance.

a. Vulnerable populations

The design of in-hospital treatment package suitable for implementation in Australian public hospital context will include consideration of the needs of Aboriginal and Torres Strait Islander patients. As such ethics approval for this project is being sought from the Aboriginal Health Research Ethics Committee.

Extensive consultation with stakeholders has taken place during the design phase of the in-hospital intervention including (but not limited to) organisations such as the Aboriginal Health Council SA, Aboriginal Health Services, the Aboriginal community controlled health sector, the Wardliparingga Aboriginal Research Unit, SAHMRI, the South Australian Aboriginal Chronic Disease Consortium (SA ACDC) Community Reference Group, Nunkuwarrin Yunti Primary Care services and the Northern Health Network to ensure that the cultural distinctiveness of Aboriginal and Torres Strait Islander communities are fully considered.

The Expert Advisory Group (**Appendix 2**) in consultation with the SA ACDC will utilise existing community evidence identified in the South Australian Aboriginal Diabetes Strategy which was developed following extensive consultation with Aboriginal Leaders and organisational stakeholders by the Wardliparingga Aboriginal Research Unit, SAHMRI and is being implemented by the SA ACDC through the SA Aboriginal Chronic Disease Consortium Road Map for Action 2017-2021.

During the consultation phase the Expert Advisory Group will seek to identify and address any potential negative consequences of the design of the in-hospital intervention for Aboriginal and Torres Strait Islander Peoples.

b. Waiver of Consent

There is no request for consent waiver.

c. Confidentiality

Participant data will be presented in a de-identified format, participants will not be identified or in publications arising from the research. Data will only be published at an aggregate level. There are no restrictions on the ability to ensure confidentiality of participants in this study, nor will there be data sharing at an individual, identifiable level.

d. Ethical Review

The study will be conducted in full conformance with principles of the “Declaration of Helsinki”, Good Clinical Practice (GCP), the National Statement on Ethical Conduct in Human Research (NHMRC, 2007), Australian Code for the Responsible Conduct of Research (2007) and within the laws and regulations Australia.

Ethical approval will be sought from the following HRECs:

- The Central Adelaide Local Health Network (CALHN)- SA Department for Health and Ageing Human Research Ethics Committee
- Aboriginal Health Research Ethics Committee (AHREC).

e. Site/Governance Review

In accordance with the *SA Health Research Governance Policy Directive*, Site Specific Assessment (SSA) Approval will be sought from Lyell McEwin hospital, NALHN and The Queen Elizabeth and Royal Adelaide Hospitals, CALHN where the project is being conducted, including.

14. OUTCOMES AND SIGNIFICANCE

The outcomes of the study will provide new information as to (i) the feasibility of an approach to identify an optimal in hospital treatment; (ii) treatments that can be initiated during a hospital stay, not directly related to the diabetes that will improve blood sugar control and reduce diabetes related distress by improving health literacy and self-efficacy and providing support, (iii) determine the barriers and enablers of an effective outcome. Ultimately, we aim to reduce the risk of subsequent admission and if admitted, length of stay.

The ultimate long-term objective is to deliver an effective in-hospital treatment package for T2DM that is suitable for implementation in an Australian public hospital context with consideration of the needs of Aboriginal and Torres Strait Islander patients, leading to a reduction in the length of hospital stays, the likelihood of readmission and greater efficiency and value within health care delivery systems, benefiting patients, healthcare providers, and care systems alike.

Appendix 1. Lyell McEwin Hospital Advertising Material Master V2.0

THE UNIVERSITY
of ADELAIDE

SAHMRI
South Australia Health &
Medical Research Institute

LYELL MCEWIN
HOSPITAL

Initiation of a novel In-hospital Treatment for patients with Type 2 Diabetes (REMIT-2D)

We invite you to participate in a research study on diabetes self-management and health literacy.

Am I Eligible?
To be in this study you need to:

- Have Type 2 diabetes
- Be over the age of 18
- Not be scheduled for a cardiac angiograph

What will I need to do?

- Fill in some questionnaires about what medication you take, your lifestyle, your social situation, how you cope with diabetes and some basic information about yourself
- Agree for limited access to your health records
- Have a blood test 6 weeks after you have been discharged home
- Agree to be contacted by the study Care Coordinator over the telephone 6 weeks after you have been discharged home to discuss how you cope with diabetes

If you are interested please contact [name] (Care Coordinator):
[contact]
Email: [contact]

Your participation in this study is completely voluntary. If you do consent to participate, you may withdraw at any time.

The study has ethics approval from the Central Adelaide Local Health Network (CALHN) Human Research Ethics Committee (Project Number HREC/19/CALHN/156) and Northern Adelaide Local Health Network research governance (SSA19/NALHN/082). For any concerns about the study, please contact the Principal Investigator [name] (The University of Adelaide) on [name].

V2_06/08/2019

Appendix 3. Educational resources to develop diabetes-related health literacy

DIABETES SELF-CARE

THE WELLNESS WHEEL

BE HEALTHY

Healthy eating, regular activity, good sleep and a healthy mind

MEDICATIONS

Take your medications regularly. Learn about the drugs you are taking.

<https://www.nps.org.au/medical-info/consumer-info/managing-your-medicines>

PRIMARY CARE

Seeing a health professional regularly can identify problems early.

HEALTH CHECKS

Weight, blood pressure, HBA1C (average blood sugar over 3mths), blood fats and urinary protein

SELF-CARE

Understanding what's normal for you and knowing when to seek help

Foot care

- Check your feet every day
- Look for ulcers, swelling, blisters, bruising, cuts- seek medical help
- See a podiatrist

EYE CARE

- Have an eye test regularly
- Seek medical help if vision worsens

DENTAL CARE

- Have regular teeth and gum checks
- Quit smoking
- No sugary drinks

MONITOR YOUR HEALTH

Weigh yourself regularly, keep a diet and activity diary, check your blood sugars.

RESOURCES

Heart Foundation Helpline ph [name] and website: <https://www.heartfoundation.org.au/healthy-eating>

Diabetes Australia Helpline ph [name] and website: <https://www.ndss.com.au/>

Healthy Star rating: designed to show the nutritional content of packaged food, but it does not mean low in sugar or healthy. Fresh whole foods, mostly plants are best. Website: <http://healthstarrating.gov.au/internet/healthstarrating/publishing.nsf/content/home>

Get Healthy, ph [name] M-F 8am-8pm website: www.gethealthy.sa.gov.au

Keep Sight Australia, website <https://www.keepersight.org.au/>

The Sleep Health Foundation, P: [name], E: [contact], Website: <https://www.sleephealthfoundation.org.au/obstructive-sleep-apnea.html>

Sleep Health Service Clinics, SA Health, Locations:

Clinic B, level 2, Flinders Medical Centre, P: [name] or First Floor, Noarlunga GP Plus Super Clinic P: [name]

Adelaide Sleep Clinic, Wellington Centre, [name], P: [name]

E: [contact]

Centre for Physical Activity and Ageing, [name] Ph [name], website: [http://sacommunity.org/org/197186Centre for Physical Activity in Ageing](http://sacommunity.org/org/197186Centre%20for%20Physical%20Activity%20in%20Ageing)

Active Ageing Australia, [name], Ph: [name], email: [contact], website: <https://activeageing.org.au/>

[figure not shown]
Depression and Anxiety

Beyond Blue, P: [name], Website: <https://www.beyondblue.org.au/>

[figure not shown]
THE WELLNESS WHEEL

BENEFITS OF HEALTHY FOOD

THINK BEFORE YOU DRINK

**ENERGIZE
MUSCLES**

**ELIMINATE
TOXINS**

**CONTROL
CALORIES**

**HEALTHY
KIDNEYS**

[figure not shown]
**IMPROVE
SKIN**

Eat Fresh Whole Foods especially Plant Based Food

Eating well is not difficult, but understanding what foods are important can sometimes be confusing. The following information provides you with tips and cues on how to improve your diet and get the benefits you are looking for.

Eat whole foods in quick steps:

- Choose Whole foods, have a look at the following and if you are choose more in the red zone, focus on changing to the green zone (some examples of swaps):

- Eat more plant foods. Does your lunch or dinner plate look like this? If not, maybe adding more fresh or frozen veggies is your first step.

- Time your meals: Avoid grazing aim to have 3 MEAL TIMES a Day and in between HYDRATE.
- Avoid Night Time Eating: Eating late at night is usually related to boredom eating. Try not eating after 8pm or at least 3 hrs before going to bed. If you get hungry, try water first, then some of your plant-based foods if you are still feeling hungry – fibre can make you feel fuller than a sweet!

Shopping Trolley Quiz

Place a number by the foods in order of what you would add to your shopping trolley.

Granola cereals ____ 	2 Minute Noodles ____ 	Frozen pies or sausage rolls ____ 	Pre-cut and packed salad mixes ____ 
Potato Crisps ____ 	Canned Tomatos 	Rotisserie Chicken 	Cereal and Nut Bars 
Regular Dressings OR sauces (BBQ or Tomato) 	Sauces (Meal) ____ 	Pre Made Lasagne 	Crumpets ____ 
Wholemeal Bread ____ 	Mixed Rice Crackers 	Salt-reduced Stock 	Fruit Juice ____ 
Dried Herbs and Spices 	Deli style Metwurst or Pepperoni ____ 	Frozen Vegetables 	Milk coffee sachets 
Frozen Waffles ____ 	Chuck Steak ____ 	Hazelnut Chocolate Spread ____ 	Shredded wheat cereals ____ 

Shopping Trolley Quiz

Outcome: Those highlighted **RED** are **NO GO** foods, best not to add them to the Trolley and the **GREEN** are the **GO TO** foods.

Granola cereals ____.
 	
2 Minute Noodles ____
 	
Frozen pies or sausage rolls ____
 	
Pre-cut and packed salad mixes ____
 

Potato Crisps ____
 	
Canned Tomatoes ____
 	
Rotisserie Chicken ____
 	
Cereal and Nut Bars ____
 

Regular Dressings OR sauces (BBQ or Tomato) ____
 	
Sauces (Meal) ____
 	
Pre Made Lasagne ____
 	
Crumpets ____
 

Wholemeal Bread ____
 	
Mixed Rice Crackers ____
 	
Salt-reduced Stock ____
 	
Fruit Juice ____
 

Dried Herbs and Spices ____
 	
Deli style Metwurst or Pepperoni ____
 	
Frozen Vegetables ____
 	
Milk coffee sachets ____
 

Frozen Waffles ____
 	
Chuck Steak ____
 	
Hazelnut Chocolate Spread ____
 	
Shredded wheat cereals ____
 

Sample Time	Meal Occasion	Meal Suggestions		Average Cost (\$)
7-8am	Meal 1	
1-2 boiled eggs + 1 cup grilled veggies (i.e. carrot, capsicum, tomato, spinach, mushroom whatever is left in your fridge)
 	
150-200g plain or vanilla yoghurt + 40g nuts/seed mix added to the yoghurt for taste and crunch.
 	\$2.50
	Hydration	*[name] can they have a coffee no sugar?		
1230-1pm	Meal 2	
Small tin flavoured Tuna + 2 cups of salad mixed in a bowl (30g cheese optional)
 		\$4.00
	Hydration			
6-7pm	Meal 3	
150-200g of cooked meat, fish, chicken and 2 Cups of salad + 30g Cheese (optional) mixed into a tossed salad + veg (add 40ml of Free salad Dressing or Oil and vinegar for dressing)
 		\$5.70
	Hydration			
Nothing after 8 pm				

MUSCLE RESISTANCE ACTIVITY

[figure not shown]
THE WELLNESS WHEEL

PHYSICAL ACTIVITY IS LIKE TOOTHBRUSHING FOR THE WHOLE BODY

- We do it everyday
- Use every opportunity to **Move, Move, Move**
- Try tracking your activity using a Fitbit, phone app. or simple pedometer (aim for 10,000 steps/day).

BENEFITS OF MUSCLE RESISTANCE ACTIVITY

And let's do some Resistance Activity.

Resistance exercise can be done at home, even while watching your favourite TV show. It is easy, fun, free and suitable for anyone

Here are 4 movements for your upper body and 4 for your lower body

Upper Body

- Sit in a high back chair
- Make sure your bottom is right at the back of the chair and your back is straight
- Hold a 1 kg weight (see resource list) in each hand. If 1kg is too heavy use a can of sweetcorn or similar ~450 grams
- Do 20 repetitions of each of the movements pictured below. Rest briefly for 1-2 minutes then do another 20 of each movement. If you cannot manage 20, do as many as you can and gradually build up to 20.
- Do the movements slowly breathing in and out with each.
- Do these at least 3 days of the week. Build up to every day

Bicep

**Overhead
shoulder**

Straight arm

Side arm

When you have completed the 2 lots of 20 repetitions of each of the 4 movements (or as many as you can do) stand and go for a walk for 10 minutes. Even if it is just around the house.

Now you are set to do the lower body

Lower Body

- For these you need 1kg strips of lead that are covered with material and have Velcro straps to fasten them around your ankles. You can also fill a small pouch with 1kg or 500 grams of course sand, attach some ties or Velcro straps so that one can be strapped around each ankle
- In the pictures below, you will see one of these exercises is done sitting in the chair as you for the upper body exercises. Two are done standing behind the chair and holding on. The final one is done lying on the bed. Maybe leave this one for last.
- Do 20 repetitions of each of the movements pictured below. Rest briefly for 1-2 minutes then do another 20 of each movement. If you cannot manage 20, do as many as you can and gradually build up to 20.
- Do the movements slowly breathing in and out with each.
- Do these at least 3 days of the week. Build up to every day.

**Knee
flexion/extension**

**Lateral leg
raise**

Toe lift

Straight leg raise

When you have completed the 2 lots of 20 repetitions of each of the 4 movements (or as many as you can do) stand and go for a walk for 10 minutes. Even if it is just around the house.

**IF AT ANY TIME YOU EXPERIENCE PAIN IN JOINTS OR THESE EXERCISES FEEL DIFFICULT,
PLEASE DISCUSS WITH YOUR HEALTH PROFESSIONAL.**

Here are some other ideas to help get you **moving moving moving**

Heart Foundation walking group join a group in your local area for free; phone [name] or [name] or go online at;

[Website: https://www.heartfoundation.org.au/support/heart-foundation-helpline](https://www.heartfoundation.org.au/support/heart-foundation-helpline)

Centre for Physical Activity and Ageing, [name] Ph [name], website:

[http://sacommunity.org/org/197186Centre for Physical Activity in Ageing](http://sacommunity.org/org/197186Centre%20for%20Physical%20Activity%20in%20Ageing)

Active Ageing Australia, [name], Ph: [name], email:

[contact], website: <https://activeageing.org.au/>

Exercise is Medicine- Australia- ESSA, Ph: [name], Email:

[contact], Website: <http://exerciseismedicine.com.au/>

Department of Health Be Active: a physical activity guide for older Australians.

Ph [name] or [name] or [name]- country

COTA SA: Ph [name] or [name] website: www.cotasa.org.au

Purchase 1 kg weights:

Rebel Sports: Gepps Cross [name], ph [name] or Tea Tree Plus, [name] ph [name] or online.

Gym and Fitness online: ph [name] or

<https://www.gymandfitness.com.au/products/>

WELLNESS WHEEL

GOOD SLEEP = GOOD HEALTH
Some benefits

Getting a Good Night's Sleep – Top Tips

A good night's sleep starts before bedtime

Don't nap during the day

**Stop caffeine after noon
Stop alcohol 3 hrs before
Avoid big meals and finish
2-3 hrs before**

Keep the room cool

[figure not shown]

**A comfortable room
without distractions**

Have a regular bedtime

***Have regular routine
and relaxation rituals***

Meditate, read or listen to music

***Keep technology out
of the bedroom***

**Stop working and turn
off computer and TV
screens 1 hour before**

IS YOUR SLEEP AFFECTED BY ANY OF THESE?

1. OBSTRUCTIVE SLEEP APNOEA (OSA):

What is it? OSA is where the airways block off during sleep, depriving the person of oxygen and can occur several times per night.

When should I seek help? if you're experiencing snoring along with waking up gasping and choking, the need to frequently urinate during the night, erectile dysfunction, feeling sleepy and fatigued during the day, dozing off in the afternoon or early evening, irritability and mood changes.

2. INSOMNIA:

What is it? Insomnia is when you can't sleep or can't sleep enough. It can be caused from medications or other drugs, alcohol, caffeine, chronic pain, stress or anxiety.

When should I seek help? if you have regular problems falling asleep, staying asleep, waking too early in the morning or worrying about being able to sleep.

3. SHIFT WORK:

Getting enough quality sleep can be difficult for people who work shift work.

What can I do?

- ensure your bedroom is dark and quiet, or wear ear plugs
- turn your phone off and let people know not to disturb you,
- avoid caffeine, alcohol and large meals,
- avoid exercise and bright sunshine just before going to sleep
- sleep before work instead of immediately afterwards,
- try to establish regular sleep routines,

RESOURCES

The Sleep Health Foundation, P: [name], **E:** [contact], **Website:** <https://www.sleephealthfoundation.org.au/obstructive-sleep-apnea.html>

Sleep Health Service Clinics, SA Health, Locations:

Clinic B, level 2, Flinders Medical Centre, **P:** [name] or First Floor, Noarlunga GP Plus Super Clinic **P:** [name]

[figure not shown]
Adelaide Sleep Clinic, Wellington Centre, [name],

P: [name] **E:** [contact]

[figure not shown]
COPING with diabetes and reducing distress

WELLNESS WHEEL

[figure not shown]

Healthy Environments- refers to your physical environment (e.g., your housing), social and cultural environment (e.g., where people are treated with respect, dignity, and equality) and having adequate finances to meet your needs.

Sense of Belonging- we all need to feel a sense of belonging in our families and communities.

[figure not shown]
Healthy Behaviours- are essential for our psychological and physical health. Having **healthy coping strategies** to use when stressed is essential for health and well-being. These include: adequate sleep, nutrition and physical exercise. We also need to have activities that we do that give us pleasure and sense of achievement

Coping- life is bumpy. Having health coping strategies to use when stressed is essential for health and wellbeing.

Resilience- is the process of bouncing back after coping with a challenging situation

Treatment of Illness- early and effective treatment of psychological and physical illnesses help to reduce the impact of them on our health and well being.

Make a coping plan with your health professional

We all get upset and distressed from time to time. When we're feeling upset, it can be hard to think clearly and make good decisions. Coping Planning helps you think ahead to plan healthy coping strategies to use to feel calmer. Your coping plan can be a reminder to use these strategies when you're upset.

Make a list of coping strategies using the My Coping Worksheet

Ask your health professional for any extra support contacts so you have it handy if you need it

[Download](#)

[My Coping Plan App for Apple or Android phones or tablets](#) and add these details so that you can keep a copy of your plan with you.

App Store Preview

This app is only available on the App Store for iOS devices.

My Coping Plan 4+

University of South Australia

★★★★★ 3.7, 6 Ratings

Free

MY COPING PLAN

Self-soothing

Things I can do on my own

People who can support me

Professionals who can support me

In an emergency

- Go to the nearest hospital emergency department
- Telephone emergency services - Triple Zero

©University of South Australia

Understanding type 2 diabetes

Type 2 diabetes is the most common form of diabetes. It affects 85–90% of all people with diabetes.

What is type 2 diabetes?

Diabetes is a condition where there is too much glucose (sugar) in the bloodstream. Glucose is an important source of energy for your body. It comes from carbohydrate foods that you eat, such as bread, pasta, rice, cereals, fruits, starchy vegetables, milk and yoghurt. Your body breaks down carbohydrates into glucose, which then enters your bloodstream.

Insulin is made in your body by the pancreas. Insulin is needed to allow glucose from the bloodstream to enter the body cells and be used for energy.

Type 2 diabetes occurs when the body resists the effects of insulin and cannot make enough insulin to maintain blood glucose levels within the target range. This leads to high blood glucose levels.

Who is at risk of type 2 diabetes?

Type 2 diabetes usually occurs in adults, but younger people – and even children – are now developing this type of diabetes.

Risk factors for type 2 diabetes include:

- ✦ having a family history of type 2 diabetes
- ✦ having pre-diabetes
- ✦ being above the healthy weight range

- ✦ having an inactive lifestyle
- ✦ increasing age
- ✦ having an Aboriginal or Torres Strait Islander background
- ✦ being from a Melanesian, Polynesian, Chinese, Southeast Asian, Middle Eastern or Indian background
- ✦ having prior gestational diabetes
- ✦ having polycystic ovary syndrome
- ✦ taking some types of antipsychotic or steroid medications.

Can type 2 diabetes be prevented or cured?

People who are at risk of type 2 diabetes can delay and, in some cases, even prevent developing diabetes by adopting a healthy lifestyle. This includes regular physical activity, making healthy food choices, and being a healthy weight.

NDSS Helpline [name]

ndss.com.au

Making healthy food choices

Healthy eating, along with regular physical activity, can help you look after your diabetes. It can also help you manage other risk factors like high blood pressure, or unhealthy cholesterol and triglyceride levels.

Healthy eating for people with diabetes is no different from what is recommended for everyone else. There is no need to prepare separate meals or buy special foods – the whole family can enjoy the same healthy meals.

There are various dietary approaches that may be suitable for people with diabetes. These include Mediterranean-style diets, low fat plant-based diets or lower carbohydrate eating plans.

The following guidelines are general recommendations suitable for most people with diabetes. However, a dietitian can help you to develop an eating plan to meet your food preferences and nutritional needs.

To make healthy food choices:

[figure not shown]
- eat regular meals to assist with managing energy and blood glucose levels
- choose high-fibre, lower glycaemic index (GI) carbohydrate foods
- limit foods that are high in saturated fat and choose healthy fats
- include lean protein foods with your meals
- choose foods low in added salt (sodium) and avoid adding salt to your food.

Eat regular meals in the right amounts

Aim to eat three meals during the day and choose serving sizes to meet your energy needs. Talk to your dietitian for advice about your individual needs and the serving sizes that are right for you.

When preparing a healthy meal aim to:

- fill half of your plate with a variety of non-starchy vegetables or salad
- fill a quarter of your plate (a palm-sized serving) with a lean protein source, such as lean meat, skinless poultry, fish, seafood, tempeh, legumes or eggs
- fill a quarter of your plate with a nutritious carbohydrate food that has a lower GI, such as wholegrain or legume pasta or noodles, brown, basmati or Doongara™ rice, quinoa, soba or mung bean noodles, legumes (such as chickpeas, kidney beans, lentils), barley, freekeh, corn, low-GI potato or sweet potato.

NDSS Helpline [name]

ndss.com.au

Physical activity

Regular physical activity is one of the most important things you can do to improve your health and help manage your diabetes.

The more physically active you are, the greater the health benefits will be. However, any activity, even at a slow pace, can have health benefits, and some activity is better than none at all.

Benefits of physical activity

Physical activity plays a vital role in helping the body use glucose as fuel for the working muscles, which in turn lowers blood glucose levels.

When the body starts to exercise, the muscles need energy to move. This energy comes from glucose in the blood as well as glucose stored in the muscles and, occasionally, from stores in the liver.

There are plenty of other benefits of regular physical activity, including:

- » reducing the risk of heart disease and stroke
- » lowering cholesterol levels
- » helping to lower blood pressure
- » assisting with weight loss and maintaining a healthy weight
- » slowing age-related loss of muscle mass
- » preventing osteoporosis and risk of falls
- » increasing strength, power and balance
- » improving mood
- » helping circulation in lower limbs.

Types of physical activity

Doing a combination of different types of physical activity has proven benefits for managing diabetes. There are two main types of physical activity: aerobic exercise and resistance exercise.

NDSS Helpline [name]

ndss.com.au

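### Minor safety improvement: the Eat Whole Foods handout gives two evening-food instructions with no exception for low blood sugar, and no stated step asks about low blood sugar in any arm

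*Protocol*

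**What the plan says.** Section 9.b assigns the Eat Whole Foods handout to groups 3 and 4. Its tips in Appendix 3 advise "Avoid grazing aim to have 3 MEAL TIMES a Day and in between HYDRATE". On evenings they say "Try not eating after 8pm or at least 3 hrs before going to bed", and then "If you get hungry, try water first, then some of your plant-based foods if you are still feeling hungry". The sample meal table in the same handout closes with "Nothing after 8 pm". The table also still holds a drafting query, "can they have a coffee no sugar".

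Groups 3 and 4, like group 2, also receive the Diabetes Self-care sheet. Its relevant lines are general: "Take your medications regularly. Learn about the drugs you are taking", "Weigh yourself regularly, keep a diet and activity diary, check your blood sugars", and a line on understanding what is "normal for you and knowing when to seek help".

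Section 7 admits adult inpatients with type 2 diabetes. The exclusions concern age, pregnancy, capacity to consent and scheduled coronary angiography; none concerns drug treatment.

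At six weeks (section 9.b) the call covers the Diabetes Distress Scale and whether the blood test has been done. A patient without a test may be offered a home visit by a blood collection nurse. A patient who cannot be reached by phone is posted the Distress Scale. Section 8 lists no low-blood-sugar outcome. Section 9.e offers medical assessment for issues that patients raise.

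**The concern.** There are two separate points.

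The first is wording. A patient in group 3 or 4 who is hungry late in the evening can find one line that allows food and another that does not. For a patient on insulin or another glucose-lowering drug, the advice not to graze, to try water first and to stop eating at 8 pm comes with no statement that low blood sugar should be treated whatever the hour. Section 1 intends the package for delivery by trained staff who are neither doctors nor nurses, so the written text carries weight.

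The second is collection. Arms are kept or dropped on change in HbA1c, yet no stated step asks every arm about low blood sugar in the same way. The stated safety route depends on the patient raising the issue, and that may differ by arm: groups 2 to 4 receive the sheet telling them to check their blood sugar and group 1 does not. An analysis plan cannot supply answers that were never collected.

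**Working it through.** The protocol gives no figure on this point to reproduce. The check is mainly a comparison of texts, followed by simple counts.

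**Evening instructions side by side**

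| Place in handout | Instruction | Food after 8 pm if hungry? | Exception for low blood sugar? |
|---|---|---|---|
| Tips | Try not to; water first, then plant-based food | Allowed | None shown |
| Sample meal table, last line | Nothing | Not allowed | None shown |

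**Is the advice particular to groups 3 and 4?** Only in part. The NDSS food sheet (groups 1 and 2) also recommends three meals a day, and the Sleep sheet (groups 2 to 4) also advises finishing meals 2–3 hours ahead of bedtime. The no-grazing advice and the 8 pm limit are particular to groups 3 and 4.

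**Does another sheet fill the gap?** The Self-care sheet gives seek-help triggers for feet and eyes. For glucose it says only to check. No sheet, as reproduced, tells patients what to do about low blood sugar.

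**Is low blood sugar asked about?** Section 8, the six-week call, the mailed alternative and section 9.e contain no such question. The Medical Patient data form and the Distress Scale items are not reproduced, so this supports only the statement that no step is stated.

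**Recipients** (section 10.a: 33 per arm per stage, 132 in stage one, 198 in all)
- Stage one: 2 × 33 = 66 of 4 × 33 = 132.
- Overall: 66 of 198 if group 2 is retained; 66 + 33 = 99 of 198 if group 3 or 4 is retained.
- The share on glucose-lowering drugs is not given. At an assumed 25% to 75%, 66 × share is about 17 to 50, and 99 × share is about 25 to 74. These would be users of any such drug, not patients shown to be at risk.

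**What a six-week question could show.** The response rate is not given. I assume 80% to 100%; the lower end matches the 20% drop-out that section 10.a expects for HbA1c. That gives 26 to 33 answers per arm at stage one, and 53 to 66 in each of the two final arms. With zero reports among n, the one-sided 95% upper limit for the true risk is 1 − 0.05^(1/n):
- n = 26: 10.9%; n = 33: 8.7%
- n = 53: 5.5%; n = 66: 4.4%

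Such counts can be described but cannot separate the arms.

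**Call time** at an assumed one minute each: 132/60 = 2.2 hours for stage one; 198/60 = 3.3 hours for the whole trial.

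**The case against.** The contradiction is mild. The tips are softly worded, and the conflicting line ends a table of sample meals, where it can be read as shorthand for the tip. The coffee query is a drafting leftover. Both are copy-editing matters. This stands and lowers the weight of the point, but it does not remove it: neither version makes an exception for low blood sugar.

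Forms that are not reproduced may already ask about low blood sugar. This also stands, and the second point is limited accordingly.

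There are safeguards. Patients are identified through ward medical and nursing staff, the coordinator answers questions, the Self-care sheet gives a medicines link and a diabetes helpline, a nurse visits some patients at home, and section 9.e provides medical assessment. These lower the stakes but do not replace a question put to everyone.

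A low-blood-sugar line placed only in the groups 3 and 4 handout would change the contrast between arms. That is right, and the line should go to all four groups.

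A reader might infer that the handout is unsafe, that it exposes groups 3 and 4 to more low blood sugar, or that the trial may select a harmful arm. The documents support none of these. They give no drug share and no episode rate, they do not link the evening advice to any event, and part of the meal-timing advice is shared across groups.

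**Conclusion.** A minor safety improvement, with medium confidence. The handout gives two evening instructions and, in the text shown, no exception for low blood sugar in patients whose treatment may call for one. No stated step asks any arm about low blood sugar. Harm is possible but not shown, and its size cannot be computed from the documents.

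The point does not affect the HbA1c estimate, the type I or type II error rates, or the rule for dropping arms. It rests on the handouts as reproduced, without their figures, and on the stated procedures, without the unseen forms. It merits action because the change is cheap and because handout wording and follow-up questions cannot be repaired at the analysis stage.

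**What to change.** 1. Make the last line of the sample meal table match the evening tip. Give all four groups the same short, clinician-agreed line: patients on insulin or other glucose-lowering drugs should treat low blood sugar at any hour, regardless of meal-timing advice. Because every group receives it, the contrast between arms is unchanged.
2. Add one standard question to the existing six-week call and mailed form in all groups: any low-blood-sugar episode since discharge, and any that needed another person's help. Refer positive answers through the section 9.e medical assessment route. Tabulate by arm descriptively, with no test and no change to the dropping rule.
3. Delete the coffee query; this is clerical tidying only.

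Cost: an ethics notification and about one minute per call (up to about 3.3 hours over 198 patients), plus any assessment triggered. No new visit or staff is needed. Section 10.a says the sample size was cut because of low accrual, so recruitment appears to be under way. There may then be two handout versions, and patients already followed up would lack the new answer. The counts will be self-reported and too small to separate the arms.
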